7.2 TNM staging

International Standard for Staging Colorectal Cancer

The American Joint Committee on Cancer (AJCC) stipulates that the staging of colorectal cancer is performed according to the TNM staging system.

1. Definition of TNM

primary tumor (T)

- TX: The primary tumor cannot be evaluated.
- T0: No evidence of primary tumor.
- Tis: Carcinoma in situ. Limited to the epithelium or invading the mucosal lamina propria.
- T1: Tumor invasion into the submucosa.
- T2: Tumor invasion of the muscularis propria.
- T3: The tumor penetrates the muscularis propria layer to reach the subserosal layer, or invades the perirectal tissues without peritoneal coverage.
- T4a: Tumor penetrates the visceral peritoneum.
- T4b: The tumor directly invades or adheres to other organs or structures.

Regional lymph nodes (N)

- NX: Regional lymph nodes cannot be evaluated.
- N0: No regional lymph node metastasis.
- N1: Metastasis to 1-3 regional lymph nodes.
- N1a: 1 regional lymph node metastasis
- N1b: There are 2-3 regional lymph node metastases.
- N1c: Tumor deposits (TD) in the subserosal, mesenteric, and peritoneally uncovered perirectal tissues, without regional lymph node metastasis.
- N2: Metastasis to more than 4 regional lymph nodes.
- N2a: Metastasis to 4-6 regional lymph nodes.
- N2b: Metastasis to 7 or more regional lymph nodes.

distant metastasis (M)

- MX: The distant metastasis status is unknown.
- M0: No distant metastasis.
- M1: distant metastasis.
- M1a: Distant metastasis is confined to a single organ or site (e.g., liver, lung, ovary, non-regional lymph nodes) but without peritoneal metastasis
- M1b: distant metastases are present in more than one organ, but without peritoneal metastases.
- M1c: Peritoneal metastasis with or without metastasis to other organs.

American Joint Committee on Cancer (AJCC) staging

Stage 0 Tis, N0, M0

Stage IA, T1, N0, M0 Stage IA, T1, N0, M0

Stage IB, T2, N0, M0 Stage IB, T2, N0, M0

Stage IIIA, T3, N0, M0 Stage IIIA, T3, N0, M0

Stage IIIB, T4a, N0, M0 Stage IIIB, T4a, N0, M0

Stage IIIC₁, T4b, N0, M0

Stage IIIA, T1-2, N1/N1c, M0 Stage IIIA, T1-2, N1/N1c, M0

T1 N2a M0

Stage IIIIB, T3-4a, N1, M0

T2-3 N2a M0

T1-2, N2b, M0	
Stage IIIIC, T4a, N2a, M0	Stage IIIIC, T4a, N2a, M0
	T3-4a, N2b, M0
	T4b, N1-2, M0
Stage IVA, any T, any N, M1a	Stage IVA, any T, any N, M1a
Stage IVB: Any T, Any N, M1b	Stage IVB: Any T, Any N, M1b
Stage IVC: Any T, Any N, M1c	Stage IVC: Any T, Any N, M1c

7.3 RECIST Tumor Assessment Criteria

In this study, the new international standard proposed by the RECIST (Response Evaluation Criteria in Solid Tumors) committee will be used to evaluate tumor response and progression. The only change in the RECIST criteria is the application of the maximum diameter of the tumor lesion (one-dimensional measurement).

Measurable lesions: Measurable lesions are defined as those that can be accurately measured in at least one dimension (with the longest diameter recorded), with a maximum diameter \geq 20 mm measured using conventional techniques (PE, CT, XR, MRI) or \geq 10 mm using spiral CT scanning. Spiral CT scans for tumor response evaluation must be reconstructed with a slice thickness of 5 mm. All tumor measurements must be recorded in millimeters (or tenths of centimeters).

Unmeasurable lesions: All other lesions (or disease sites) excluding measurable lesions, including small lesions (measured by conventional techniques with a maximum diameter <20 mm or by spiral CT with a maximum diameter <10 mm), are considered unmeasurable. Lesions in bones, meninges, ascites, pleural/pericardial effusions, cutaneous lymphangitis/pneumonia, inflammatory breast diseases, abdominal masses (unfollowable by CT or MRI), and bladder lesions are all deemed unmeasurable.

Target lesions: A maximum of 2 lesions from each organ's measurable lesions may be selected as target lesions, with up to 5 representative lesions from all affected organs eligible for selection. All target lesions must be recorded and measured during the baseline phase. These 5 lesions should be chosen based on their size (longest diameter of the lesion) and the reproducibility of their precise measurements (whether via imaging techniques or clinical measurements). The sum of the longest diameters (LD) of all target lesions will serve as the baseline total LD. The baseline total LD will be used as a reference value to

objectively evaluate tumor response by measuring the size of subsequent lesions. If more than 5 measurable lesions are available, those not selected as target lesions will be classified as non-target lesions along with unmeasurable lesions.

Non-target lesions: include all non-measurable lesions (or disease sites) and all measurable lesions outside the selected 5 target lesions. These lesions do not require measurement but should be recorded as "present" or "absent" at baseline and at each follow-up.

Efficacy Evaluation: All patients will undergo one of the following efficacy evaluations:

Complete remission (CR): All clinical and imaging evidence of the tumor (including target and non-target lesions) is eliminated.

Partial response (PR): A reduction of at least 30% in the sum of LD values at the target lesion compared to baseline total LD.

Stable Disease (SD): A stable state of the disease. The lesion has not met the PR criteria for shrinkage or has not met the PD criteria for progression.

Disease progression (PD): Referring to the minimum total LD value recorded from the start of treatment, the sum of LD in the measured lesions increases by at least 20% or one or more new lesions appear. The emergence of any new lesions indicates disease progression. In special cases, unmeasurable lesions with clear progression may also be accepted as evidence of disease progression.

Evaluation of therapeutic efficacy for target lesions versus non-target lesions

Target lesion	Non-target lesions	New lesion	Overall response	This type of optimal response also requires
CR	CR	not have	CR	Confirm after 4 weeks
CR	Non-CR/Non-PD	not have	PR	Confirm after 4 weeks
PR	Non-PD	not have	PR	
SD	Non-PD	not have	SD	At least 4 weeks from the baseline period
PD	any	Present or absent	PD	No SD, PR, or CR had occurred previously.
any	PD	Present or absent	PD	

any	any	have	PD	
-----	-----	------	----	--

Patients with an overall deterioration in health status requiring treatment discontinuation should be reported as 'symptom exacerbation' if there is no objective evidence of disease progression at this time. Objective disease progression should be observed and documented as closely as possible even after treatment cessation.

Relief time

The duration of remission should be calculated from the time of the first meeting of the criteria for CR or PR (whichever is recorded first) until the date of the first recorded disease recurrence or progression.

disease stable time

The duration of disease stability should be calculated from the start of treatment until disease progression is achieved, with the minimum measured lesion size after treatment initiation serving as the reference.

measuring method

The same evaluation criteria and measurement techniques should be used to describe and report each designated lesion during both the baseline and follow-up periods.

Clinical lesions — Clinical lesions are considered measurable only when located on the body surface (e.g., skin nodules, palpable lymph nodes). For dermatological lesions, it is recommended to document them with color photographs including the lesion and the measuring ruler used.

Chest X-ray — When the lesion has well-defined margins and is surrounded by air-filled lung tissue, the lesion observed on chest X-ray may be considered measurable. However, CT should still be the preferred modality.

CT/MRI — CT and MRI are currently the most feasible and reproducible methods for measuring target lesions selected for response evaluation. Conventional CT and MRI should be performed with continuous scanning at a slice thickness of 10 mm or less. Spiral CT should be performed with continuous scanning at a slice thickness of 5 mm and reconstruction. This method is suitable for the chest, abdomen, and pelvis. Scanning of the head, neck, and limbs often has specific requirements.

When measurable tumor lesions meet the criteria for remission and disease stability, cytological examination must be performed for any effusion that occurs or worsens during

treatment to confirm whether it is tumor-induced (the effusion may be a side effect of treatment), thereby distinguishing between disease remission/stability and disease progression.

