Name of the principal investigator at the sub-center:

Signature: Date: Year Month Day

Signature: Date: Year Month Day

Sponsor/Lead Organization

corporate name		Changzheng Hospital Affiliated to Naval Medical University	
project leader		[name]	
Contact address	[name]	zip code	200003
[contact]	cellphone	[name]
portraiture	[name]	E-mail	[contact]

Cooperative Unit

Company/Unit Name		Innovent Biologics (Suzhou) Co., Ltd.	
project leader			
Contact address		zip code	
telephone		cellphone	
portraiture		E-mail	

Company/Unit Name		Chia Tai Tianqing Pharmaceutical Group Co., Ltd.	
project leader			
Contact address		zip code	
telephone		cellphone	
portraiture		E-mail	

scenario summary	
scenario name	A phase II study of anlotinib plus sintilimab as first-line treatment for advanced non-liver metastatic colorectal cancer
Program number	APICAL-CRC2
version number	1.0
date	2025-12-8
Sponsor	Shanghai Changzheng Hospital
indication	Advanced colorectal cancer
Estimated study duration	The study is scheduled from December 2025 to December 2026. Enrollment for this research project is planned to commence in December 2025 and is expected to conclude in December 2026. Data analysis will be completed in June 2026, with the total trial duration approximately 1.5 years.
purpose of research	The efficacy of anlotinib combined with sintilimab as first-line therapy for advanced non-hepatic metastatic colorectal cancer was evaluated using the investigator-assessed objective response rate (ORR).
Total number of cases	The sample size calculation was based on the margin of confidence compared with historical controls, assuming an ORR of 70% in this study and an ORR rate of 50% in the historical controls. In the ITT analysis set, according to the Simon two-stage design, with a one-sided $\alpha=0.05$ and statistical power=0.8, the calculated sample size was 37 cases.

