3.3.1 Eligibility Criteria

- patients with advanced colorectal adenocarcinoma confirmed by histology or cytology;
- patients without liver metastases and who have explicitly refused chemotherapy;
- those who have not received systematic therapy or have developed metastasis or recurrence 12 months after the end of adjuvant therapy;
- The patient has at least one measurable lesion (according to RECIST 1.1 criteria);

- Patients who had received local radiotherapy at least 3 weeks prior to initial drug therapy were eligible for enrollment; however, RECIST-evaluated lesions must not be within the radiotherapy field.
- The patient must be ≥ 18 years of age;
- The ECOG physical status score was 0-1;
- Life expectancy ≥ 12 weeks;
- Patients must be able to understand and voluntarily sign a written informed consent form;
- Women of childbearing age must have a negative pregnancy test result within 7 days prior to initiating treatment. Both the patient and their spouse must use contraception during the study period.

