5.1.3.2 Secondary Efficacy Analysis

The depth of response (DpR) is defined as the percentage of maximum tumor shrinkage achieved during treatment compared to baseline. If a complete response (CR) is observed, the DpR is recorded as 100%.

Tumor response and disease progression will be assessed by investigators according to the RECIST criteria.

Progression-free survival (PFS) is defined as the time from randomization to tumor progression or death, with tumor progression recorded promptly.

Overall survival (OS) is defined as the time from randomization to death from any cause.

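### Appendix 7.3 measures every lesion, lymph nodes included, by longest diameter and has no nodal axis, threshold or normal-size rule, so PR, CR and depth of response can be misclassified in patients with nodal disease

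*Protocol*

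**What the plan says.** **Measurement (Protocol 7.3).** The appendix states that "Measurable lesions are defined as those that can be accurately measured in at least one dimension (with the longest diameter recorded"), with a minimum of 10 mm on spiral CT and 20 mm with conventional techniques. Target lesions are chosen by longest diameter and by how reproducibly they can be measured, with at most two per organ and five in all. Their longest diameters are added to give the baseline sum. Non-target lesions are not measured and are recorded only as present or absent.

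**Response (Protocol 7.3).** PR is a fall of at least 30% in the sum. CR is defined as: "All clinical and imaging evidence of the tumor (including target and non-target lesions) is eliminated". In the response table, target CR combined with a non-target result short of CR gives an overall PR.

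**Depth of response (Protocol 5.1.3.2, likewise 3.7.1).** DpR is the largest percentage shrinkage from baseline, and "If a complete response (CR) is observed, the DpR is recorded as 100" per cent.

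**Lymph nodes.** The only mention in 7.3 concerns surface lesions: "Clinical lesions are considered measurable only when located on the body surface (e.g., skin nodules, palpable lymph nodes"). Nodes are not in the appendix's list of unmeasurable disease, so the general rule covers them. The staging table in 7.2 names non-regional nodes as a metastatic site.

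**Version.** Section 3.3.1 and the synopsis require RECIST 1.1 for eligibility: "The patient has at least one measurable lesion (according to RECIST 1.1 criteria"). Section 3.7.1 and appendix 7.3 refer to RECIST for response without a version, and 7.3 describes the sole change in the criteria as the use of the maximum diameter.

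**The concern.** Most tumour deposits are abnormal tissue, so full regression means that they disappear. A lymph node is a normal structure that remains on the scan when it is healthy. A rule that sums longest diameters and tests CR by elimination does not fit it without an added definition of normal size.

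Two problems follow:

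- **PR.** With no nodal threshold, a borderline node of 10 mm or more in longest diameter on spiral CT can be taken as a target. If it does not change, it stays in both the baseline and follow-up sums and dilutes the percentage fall.
- **CR and DpR.** When an involved node returns to normal size, the text does not say whether it still counts as evidence of tumour.

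PR feeds ORR, the primary endpoint, and DpR is a secondary endpoint. Liver metastases are excluded, so nodes are among the remaining metastatic sites, and response is judged by the investigators. This is not detail left for the SAP: the appendix sets out a full rule set, and that rule set does not suit one type of lesion.

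**Working it through.** **Inputs from the documents.** From 7.3: longest diameter for all lesions, PR at a 30% fall in the sum, and the CR definition. From 3.7.1 and 5.1.3.2: DpR of 100% at CR. From the synopsis: the design figures, "assuming an ORR of 70% in this study and an ORR rate of 50% in the historical controls", a sample size found "according to the Simon two-stage design, with a one-sided" alpha of 0.05, and "statistical power=0.8, the calculated sample size was 37 cases".

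**Assumed inputs (not in the documents).** Node of 10 to 14 mm longest diameter, other target disease summing to 20 to 80 mm, and a single involved node going from 25 mm to a normal 8 mm. These are illustrations only.

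**Step 1: the plan's own figure.** Exact enumeration of Simon two-stage designs for 50% against 70% gives a minimax design that stops at 12 or fewer responses in 23 and needs at least 24 in 37. Its exact one-sided alpha is 0.0482 and its power 0.801. N = 37 is therefore reproduced. A nodal rule does not enter this calculation and does not change N.

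**Step 2: PR with a static node.** Let the tumour sum be T and the node N, with N unchanged. PR requires T × s ≥ 0.30 × (T + N), so the tumour must shrink by s = 0.30 × (T + N) / T.

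| T (mm) | N = 10 mm | N = 12 mm | N = 14 mm |
|---|---|---|---|
| 20 | 45% | 48% | 51% |
| 30 | 40% | 42% | 44% |
| 50 | 36% | 37.2% | 38.4% |
| 80 | 33.8% | 34.5% | 35.2% |

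For T = 20 and N = 12: 0.30 × 32 / 20 = 48%. For T = 50 and N = 12: 0.30 × 62 / 50 = 37.2%. Without the node the figure is 30%.

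**Step 3: the opposite direction.** If the node itself falls from N to M, the requirement becomes s = [0.30 × (T + N) − (N − M)] / T. With T = 20, N = 12 and M = 8 this is (9.6 − 4) / 20 = 28%, below 30%. If a 10 mm node is the only target, a change of 3 mm is 3 / 10 = 30% and meets PR. The missing rule can therefore add responders as well as remove them.

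**Step 4: CR and DpR.**

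- *Target node alone, 25 to 8 mm.* The measured fall is 1 − 8/25 = 68%. If the residual node counts as imaging evidence, the result is PR with DpR 68%. If the reader judges that no tumour evidence remains, it is CR with DpR 100%.
- *Static node, all other target disease gone.* The fall is T / (T + N): 20/34 = 59% at the low end, 80/90 = 89% at the high end, and 50/62 = 80.6% for 50 + 12 mm. If the reader records CR instead, DpR is 100%.
- *Non-target node back to normal size.* If recorded as present, the response table gives PR. If recorded as absent, it allows CR.

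In every one of these cases the fall is at least 59% or the table gives PR, so the patient remains a responder. Only the CR share and DpR move.

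**Step 5: trial-level size.** This would need the share of patients with nodal targets, the sizes of nodes and tumours, and how the nodes behave on treatment. The documents give none of these.

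**The case against.** **Target selection concerns tumour.** Appendix 7.3 speaks of tumour lesions and representative lesions from affected organs, so a node known to be normal should not be chosen, and choosing by size favours larger lesions. This stands in part. The dilution in step 2 arises only when a borderline node is taken as disease, and the appendix offers no size criterion to help the reader decide.

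**CR is not blocked.** A reader might infer that a patient with a residual node can never reach CR or a DpR of 100%. The text does not go that far: it asks that evidence of the tumour be eliminated, and an investigator may hold that a normal-sized node is no such evidence. DpR is then 100% by rule. The fault is that the decision is left to each reader.

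**A downward bias in ORR is not shown.** A reader might infer that the rule lowers the primary endpoint and costs power. Static nodes do dilute shrinkage, but regressing nodes or small measurement changes push the other way (step 3), and a lost CR still counts as PR. A power loss could be quoted only by assuming the affected share, lesion sizes and a distribution of shrinkage, none of which the documents supply. The 70% design value is itself an observed subgroup ORR from the earlier trial (section 1). If nodes were measured the same way there, any dilution is already in it, and the protocol does not say.

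These objections limit direction and size. They do not remove the missing rule or the mismatch in version.

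**Conclusion.** The point holds as a defect in how response is defined. Appendix 7.3 applies a longest-diameter rule and a disappearance test to lymph nodes without an axis, threshold or normal-size rule, while eligibility rests on RECIST 1.1. Two investigators reading the same scan under 7.3 can reach different PR, CR or DpR results and both be following the text.

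For a single patient, under the assumed sizes, the shrinkage needed for PR rises from 30% to between 37% and 48% with a static 12 mm node beside 20 to 50 mm of tumour, and to between 34% and 51% over the wider range. The same regressed node can give a DpR of 68% or 100%. At trial level, neither the sign nor the size of the effect on ORR can be derived, and N = 37 is not affected. The point is worth correcting because it touches the primary endpoint and is cheap to settle, not because a particular bias has been demonstrated.

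**What to change.** Before the first response assessment, reconcile appendix 7.3 with the version named in section 3.3.1. State that RECIST 1.1 applies to measurability, target selection, response and DpR, and name the version in 3.7.1 and 5.1.3.2 as well. Write its lymph-node rule into 7.3:

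- nodes measured by short axis, with the short axis entered in the sum;
- the size above which a node may be a target;
- the size at which a node, target or non-target, counts as normal and so towards CR;
- DpR of 100% when CR is reached in this way.

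Take the thresholds from the published standard; the protocol does not reproduce them, and none is proposed here.

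The cost is a few sentences and one short-axis field in the CRF, read from the same scans. No extra imaging, readers or patients are needed. The small downside is that slightly fewer nodes will qualify as target lesions.

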3.7.1 Efficacy Indicators

Objective response rate (ORR) refers to the proportion of patients whose tumors shrink to a certain extent and sustain this reduction for a specified duration (primarily for solid tumors). It encompasses cases of complete response (CR) and partial response (PR).

Deepness of response (DpR): This refers to the percentage of maximum tumor shrinkage achieved during treatment compared to baseline. If a complete response (CR) is observed, the DpR is 100%.

Tumor response and disease progression will be assessed by investigators according to the RECIST criteria.

Progression-free survival (PFS) refers to the time from enrollment until tumor progression or death.

Overall survival (OS) refers to the time from randomization to death from any cause.

The duration of response maintenance was calculated for all patients who achieved confirmed RECIST-standardized PR or CR. The response maintenance period was defined as the time from the first recorded PR or CR until death or disease progression (whichever occurred first). For patients who were still alive and disease-free as of the analysis date, the cutoff date was set as the date of their last radiological assessment.

This study also explores the relationship between molecular markers and therapeutic efficacy and safety.

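### The endpoint sections name no RECIST version, and the appendix PD rule sets no minimum absolute growth, so a 1–3 mm change can end PFS in responders with small nadir sums

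*Protocol*

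**What the plan says.** Section 3.3.1, like the protocol summary, fixes a version for entry: "The patient has at least one measurable lesion (according to RECIST 1.1 criteria". The endpoint sections do not. Section 3.7.1 states "Tumor response and disease progression will be assessed by investigators according to the RECIST criteria". Section 5.1.3.2 repeats this, and 5.1.1 also refers to RECIST without a number.

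Appendix 7.3 states that "the new international standard proposed by the RECIST (Response Evaluation Criteria in Solid Tumors) committee will be used to evaluate tumor response and progression". It gives no version and then sets out its own rules:

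- Lesions of at least 10 mm on spiral CT are measurable, sizes are recorded in millimetres (or tenths of a centimetre), and up to five target lesions are summed.
- PR is "A reduction of at least 30% in the sum of LD values at the target lesion compared to baseline total LD".
- PD is judged against the nadir ("Referring to the minimum total LD value recorded from the start of treatment") and is met when "the sum of LD in the measured lesions increases by at least 20% or one or more new lesions appear". Clear progression of unmeasurable lesions may also count.

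Neither 7.3 nor any other section sets a minimum absolute increase for PD. Under 3.7.1, progression ends both PFS and the duration of response.

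**The concern.** There are two linked problems. First, nothing says whether the version named for entry also governs the endpoints, or whether 7.3 is meant to be that version. An assessor who follows 7.3 and one who follows RECIST 1.1 can both claim to follow the protocol.

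Second, a purely relative rule measured from the nadir becomes more sensitive as the tumour shrinks. The better the response in a patient with little measurable disease, the smaller the change that counts as progression, until it is close to the unit in which lesions are recorded. Measurement variation alone can then end a patient's PFS and response duration. The error runs one way, towards PFS and response durations that are too short, and it falls on responders with low tumour burden.

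**Working it through.** **Inputs from the protocol.** PR is a decrease of at least 30% from baseline, and PD an increase of at least 20% over nadir (7.3). The smallest measurable lesion is 10 mm on spiral CT (7.3), one measurable lesion is enough for entry (3.3.1), and scans are every 6 weeks on treatment (3.7.3.2).

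**The plan's own figure.** The protocol gives no figure for the reliability of the PD call. Its one derived number, 37 patients for ORR 50% versus 70% (one-sided alpha 0.05, power 0.80), reproduces as the minimax Simon design: 12/23 at stage one, 23/37 overall, alpha 0.0482, power 0.8011. It does not depend on the PD rule.

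**Step 1: smallest growth called PD.** Nadir = baseline sum × (1 − shrinkage). PD threshold = 0.20 × nadir.

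| Baseline sum (mm) | Shrinkage | Nadir (mm) | Growth called PD (mm) |
|---|---|---|---|
| 10 | 30% | 7 | 1.4 |
| 10 | 50% | 5 | 1.0 |
| 20 | 50% | 10 | 2.0 |
| 30 | 50% | 15 | 3.0 |
| 50 | 50% | 25 | 5.0 |
| 100 | 30% | 70 | 14.0 |

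In whole millimetres, the first row means that a recorded rise of 2 mm is PD (8/7 = 1.14 is not; 9/7 = 1.29 is). This step needs no assumption beyond the protocol's thresholds.

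**Step 2: where a minimum would matter.** A 5 mm minimum changes the call only if 0.20 × nadir < 5, that is, if the recorded nadir is below 25 mm. For a patient who just reaches PR, the baseline sum must be below 25/0.7 = 35.7 mm. At 50% shrinkage it must be below 25/0.5 = 50 mm.

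**Step 3: illustration of false PD.** The documents give no measurement error, so a range is assumed. The true sum stays at its nadir S, and every scan, including the nadir scan, records S plus an independent normal error with the stated SD on the sum. Four further scans (24 weeks) are each compared with the running minimum, in 200,000 simulated patients per setting. The entries are the chance of at least one false PD.

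| SD on the sum | S = 10 mm | S = 15 mm | S = 20 mm | With a 5 mm minimum (all three S) |
|---|---|---|---|---|
| 0.5 mm | 4% | 0.1% | 0% | about 0% |
| 1.0 mm | 50% | 18–19% | 4% | about 0.2% |
| 1.5 mm | 74–75% | 50% | 27% | about 7% |
| 2.0 mm | 85% | 68–69% | 50% | about 25% |

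At S = 30 mm the two rules give practically the same result (about 4% at SD 1.5 mm, 0.1% at SD 1.0 mm).

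**Step 4: which endpoints are exposed.** PFS and response duration end at PD, so they are exposed directly. PR is judged against baseline, so the nadir rule does not define response. ORR is touched only if a false PD comes before a confirmation scan that is required. Section 3.7.1 speaks of confirmed responses when it defines duration. In the 7.3 table as available, the confirmation cell of the row with target-lesion PR is empty, which may be a loss in text extraction.

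**The case against.** The strongest reply is that a 20% rule over nadir is explicit and workable, so an absolute minimum is a design preference, and the percentages describe a subgroup of unknown size under an assumed error. Much of this stands. The documents give no baseline sums, up to five target lesions may be summed, and at an SD of 0.5 mm the false-PD risk is 4% even at a 10 mm nadir. At an SD of 2.0 mm a 5 mm minimum still leaves about 25%. Step 3 is therefore an illustration and not an estimate of the effect on this trial's PFS. Step 1 does not depend on it.

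A reader might also infer more than the documents support:

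- *That small nadir sums will be common because a 70% ORR is expected.* ORR says how many tumours shrink by at least 30%, not how large they are.
- *That patients will be taken off treatment.* Section 3.6.1 allows treatment to continue after imaging progression if the physician sees clinical benefit. It does not alter the endpoint call.
- *That 7.3 contradicts RECIST 1.1.* The text of RECIST 1.1 is not in the documents. What they show is that the link is missing.
- *That a change smaller than one slice is noise.* Section 7.3 requires "Spiral CT scans for tumor response evaluation must be reconstructed with a slice thickness of 5 mm", but nothing there equates slice thickness with the precision of a measured diameter.

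Section 7.3 does ask for the same criteria and techniques for each lesion at baseline and follow-up. That secures consistency within a lesion, but it neither names a version nor sets a minimum.

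**Conclusion.** The point holds in a limited form. The protocol names RECIST 1.1 for entry only and leaves the endpoints to an unversioned appendix. That appendix's PD rule lets a change of 1–3 mm count as progression when the nadir sum is about 5 to 15 mm. Both facts follow from the text and its own thresholds.

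The consequence is a risk of false progression that shortens PFS and duration of response in low-burden responders. Its size depends on two quantities that the documents do not give: the measurement SD and the share of patients with recorded nadir sums below 25 mm. Across SDs of 0.5 to 2.0 mm, the illustrated risk over four scans runs from 4% to 85% at a 10 mm nadir and from 0% to 50% at 20 mm, assuming stable disease and independent errors. The sample size of 37 is untouched, and the documents do not show that the primary endpoint is compromised. The point merits correction because the wording is cheap to repair and the affected endpoints are named secondary or response-duration measures.

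**What to change.** State in 3.7.1, 5.1 and 7.3 that one version, RECIST 1.1 as eligibility already names, applies to eligibility, response and progression, and make the rules in 7.3 match that version. Have the PD endpoint definition require, besides the 20% increase over nadir, a minimum absolute increase in the sum, for example 5 mm. If the adopted version sets its own minimum, use that one. This concerns the endpoint call only and leaves the treatment provisions of 3.6.1 as they are.

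The cost is wording, with no additional scans or patients and no change to the sample size. The downside is that a few true progressions in small tumours would be called one scan later, 6 weeks on the on-treatment schedule.
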